1.1 Study Synopsis

Protocol Title	Safety of Furosemide in Premature Infants at Risk of Bronchopulmonary Dysplasia (BPD)
Phase:	II
Protocol Version	Version 5.0, 7 April 2015
Product	Furosemide
Objective	Primary: Describe the safety of furosemide in premature infants at risk of BPD Secondary: Preliminary effectiveness and pharmacokinetics (PK) of furosemide
Study Design	Multi-center, randomized, placebo-controlled, dose escalating, double masked, safety study

Study Population	
Inclusion Criteria
 
 1. Documented informed consent from legal guardian, prior to study procedures 2. Receiving positive airway pressure (nasal continuous airway pressure, nasal intermittent positive pressure ventilation, or nasal cannula flow > 1LPM) or mechanical ventilation (high frequency or conventional) 3. < 29 weeks gestational age at birth 4. 7-28 days postnatal age at time of first study dose 
Exclusion Criteria
 
 1. Exposure to any diuretic ≤ 72 hours prior to first study dose 2. Previous enrollment and dosing in current study, “Safety of Furosemide in Premature Infants at Risk of Bronchopulmonary Dysplasia” 3. Hemodynamically significant patent ductus arteriosus, as determined by the investigator 4. Major congenital anomaly (e.g. congenital diaphragmatic hernia, congenital pulmonary adenomatoid malformation) 5. Meconium aspiration syndrome 6. Known allergy to any diuretic 7. Serum creatinine >1.7 mg/dl < 24 hours prior to randomization 8. BUN >50 mg/dl < 24 hours prior to randomization 9. Na <125 mmol/L < 24 hours prior to randomization 10. K ≤2.5 mmol/L < 24 hours prior to randomization 11. Ca ≤ 6 mg/dL < 24 hours prior to randomization 12. Indirect bilirubin >10 mg/dl < 24 hours prior to randomization 13. Any condition which would make the participant, in the opinion of the investigator, unsuitable for the study 																												
Number of Participants	120																												
Number of Sites	Approximately 30 sites																												
Duration of Participation:	Up to 35 days (28 days of study drug plus 7 days of safety monitoring). Information about hospitalization will be collected at 36 weeks post menstrual age and/or at discharge.																												

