9.1 Adverse Events

An **adverse event** (AE) is any untoward medical occurrence in humans, whether or not considered drug-related, which occurs during the conduct of a clinical trial. (Any change in clinical status, routine labs, x-rays, physical examinations, etc.), that is considered clinically significant by the study investigator is considered an AE.

Suspected adverse reaction is any adverse event for which there is a reasonable possibility that the drug caused the adverse event. A reasonable possibility implies that there is evidence that the drug caused the event.

Adverse reaction is any adverse event caused by the drug.

Serious adverse event or serious suspected adverse reaction or serious adverse reaction as determined by the investigator or the sponsor is any event that results in any of the following outcomes:

1. Death at or before 36 weeks PMA

2. Life-threatening AE (“life-threatening” means that the study participant was, in the opinion of the investigator or sponsor, at immediate risk of death from the reaction as it occurred and required immediate intervention)
3. Persistent or significant incapacity or substantial disruption of the ability to conduct normal life functions
4. Inpatient hospitalization or prolongation of existing hospitalization
5. Important medical event that may not result in one of the above outcomes, but may jeopardize the health of the study participant or require medical or surgical intervention to prevent one of the outcomes listed in the above definition of serious event

All AEs will be coded using the Medical Dictionary for Regulatory Activities (MedDRA) central coding dictionary. All AEs and SAEs will be summarized by dose groups.

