9.2 Clinical Laboratory Evaluations

Hematology and chemistry parameters will be summarized at baseline (prior to first dose) and last dose, as well as change from baseline to last dose. Tables (by dose groups) will present n, mean, median, minimum, and maximum at baseline, last dose, last day of 7-day safety follow-up period, 36 weeks PMA and change from baseline to last dose. A summary of result assessment shifts from baseline to last dose will be given for each dose group for each parameter. Each parameter will be coded as abnormal and clinically significant (“ABN, CS”) or abnormal and not clinically significant (“ABN, NCS”). The number and percentage of subjects in each dose group in each shift category from baseline to last dose will be shown for each parameter.

Laboratory values at baseline, last dose and changes from baseline to last dose will also be summarized descriptively by dose groups using box plots. The box will represent the 75th and 25th percentiles and the upper and lower whiskers will represent the 95th and 5th percentiles. Mean, median and outliers will be identified. On each box plot, the number available, mean and median will also be presented numerically.

This will be completed for hematology laboratory test (including platelets) and chemistry laboratory test (including alkaline phosphatase, bicarbonate, bilirubin (direct), bilirubin (total), bilirubin (indirect), BUN, caffeine, calcium (ionized), calcium (total), chloride, creatinine, magnesium, phosphorus, potassium, sodium).

The laboratory events of interest will be summarized by dose groups. The laboratory adverse events of interest are listed in Table 3. Any abnormal laboratory values indicating serum electrolytes, renal dysfunction and other dysfunction are captured as laboratory adverse events of interest.

Table 7: Laboratory event values [4]

Laboratory values	Adverse event	Serious adverse event
Serum electrolytes		
Hypernatremia(Sodium)	150–159 mmol/L	> 159 mmol/L
Hyponatremia(Sodium)	120–124 mmol/L	<120 mmol/L
Hyperchloremia(Chloride)	110–120 mmol/L	> 120 mmol/L
Hypochloremia(Chloride)	80–90 mmol/L	< 80 mmol/L
Hyperkalemia(Potassium)	7.0–7.9 mmol/L	>7.9 mmol/L
Hypokalemia(Potassium)	2.0–2.5 mmol/L	<2.0 mmol/L
High Bicarbonate levels (Bicarbonate)	30–45 mmol/L	> 45 mmol/L

Low Bicarbonate levels(Bicarbonate)	12–14 mmol/L	< 14 mmol/L
Hypercalcemia (iCa)	1.3–1.6 mmol/L	>1.6 mmol/L
Hypocalcemia (iCa)	0.7–1.05 mmol/L	< 0.7 mmol/L

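### The laboratory event table, as printed, puts platelet counts above 1000 × 10⁹/L in neither column and cannot class infants who have only total calcium results

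*SAP*

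**What the plan says.** SAP section 9.2 holds a table of laboratory event values with one column for AEs and one for SAEs. (It is labelled Table 7, while the text calls it Table 3.)

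- **Platelets, high:** AE 450–1000 × 10⁹/L; SAE >100010 × 10⁹/L.
- **Calcium:** the two row labels begin "Hypercalcemia (iCa" and "Hypocalcemia (iCa", so both are ionized. High: AE 1.3–1.6, SAE >1.6 mmol/L. Low: AE 0.7–1.05, SAE <0.7 mmol/L. There is no row for total calcium.
- **Parameters analysed:** the same section lists "calcium (ionized), calcium (total), chloride, creatinine, magnesium, phosphorus, potassium, sodium" among the chemistry tests, so both calcium measures are collected and summarised.
- **General sentence:** "Any abnormal laboratory values indicating serum electrolytes, renal dysfunction and other dysfunction are captured as laboratory adverse events of interest". It gives no numeric limit.
- **AE definition:** under section 9.1, a laboratory change "that is considered clinically significant by the study investigator is considered an AE". Seriousness there is "as determined by the investigator or the sponsor is any event that results in any of the following outcomes", so it rests on outcome and not on a laboratory value.
- **Entry criterion (section 1.1):** "Ca ≤ 6 mg/dL < 24 hours prior to randomization". The fraction is not named.
- **Outputs (section 13):** Table 14.3.2, the laboratory event counts per dose group, uses the safety population and cites listings 16.2.9.1 and 16.2.9.2 as its source. These are the haematology and chemistry measurements. It does not cite the AE listing, 16.2.8.1.

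**The concern.** The table is the plan's only numeric rule for sorting laboratory values into AE and SAE classes. It feeds Table 14.3.2, and section 4.2 also has laboratory adverse events tabulated by cohort at the interim safety reviews. Safety is the primary objective, so the rule should give every graded analyte one class and no holes.

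Two places fail that test. If the platelet limit is programmed as printed, a count of 460 is an AE and a count of 1200 is nothing. And an infant whose calcium was followed only as total calcium can never have a calcium event in Table 14.3.2, whatever the value. If that infant stays in the denominator, the reported calcium event rate is too low.

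**Working it through.** **1. Does the SAE limit adjoin the AE band in each row?** For high-value rows, compare the SAE limit with the top of the AE band; for low-value rows, compare it with the bottom.

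- High rows (12): sodium 159/159, chloride 120/120, potassium 7.9/7.9, bicarbonate 45/45, ionized calcium 1.6/1.6, magnesium 6.0/6.0, phosphorus 12.5/12.5, bilirubin 30/30, BUN 100/100, creatinine 2.5/2.5, alkaline phosphatase 1400/1400. These 11 adjoin. Platelets 1000/100010: a gap.
- Low rows (8): sodium 120/120, chloride 80/80, potassium 2.0/2.0, ionized calcium 0.7/0.7, magnesium 1.0/1.0, phosphorus 1.0/1.0, platelets 50/50. These 7 adjoin. Bicarbonate 12/14: an overlap.

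Total: 11 + 7 = 18 adjoining rows, one gap and one overlap, out of 20. Read literally, the gap takes in every platelet count above 1000 and up to 100010 × 10⁹/L. With a limit of >1000 it closes. The bicarbonate overlap (12 to below 14 mmol/L is both AE and SAE) is a separate inconsistency that the sponsor must also reconcile.

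**2. Which calcium fraction does the entry criterion use?** Convert with mmol/L = mg/dL × 10 / 40.08, where 40.08 is the molar mass of calcium (a physical constant, not an SAP figure):

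6 × 10 / 40.08 = 1.50 mmol/L.

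As an ionized value this lies inside the table's own hypercalcemia AE band (1.3–1.6 mmol/L). A low-calcium exclusion at that level makes sense only as total calcium. This is an inference from the units, not something the SAP states.

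**3. Do entry limits equal event limits in this plan?** Not in general.

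- Sodium: entry barred <125, AE 120–124 (they meet).
- Potassium: entry barred ≤2.5, AE 2.0–2.5 (they meet).
- BUN: entry barred >50, AE from 60.
- Bilirubin: entry barred >10 (indirect), AE from 20 (fraction not named).
- Creatinine: entry barred >1.7, AE from 1.5.

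So the entry limit for calcium cannot simply be taken over as the event limit.

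**4. How large could the calcium effect be?** Let f be the share of infants with total calcium only. Assume they stay in the denominator and have the same event risk as the others. Then observed rate = (1 − f) × true rate. Neither f nor the true rate is in the SAP. For an assumed true rate of 20%:

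- f = 0: 20%
- f = 0.2: 0.8 × 20% = 16%
- f = 0.5: 0.5 × 20% = 10%

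In a dose group of 30 and with f = 0.5, that is 3 infants with an event instead of 6. This shows the mechanism only; f may be zero.

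**The case against.** The strongest reply has four parts.

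- **The platelet figure is an obvious slip.** It looks like 1000 followed by a stray 10 from the unit, possibly introduced when the PDF was read. The other rows show what was meant, and a programmer would probably notice. This stands as an explanation, and it is why the source must be checked first. It does not make the printed limit usable.
- **The values are not lost.** A reader might infer that dangerous results go unreported. The documents do not support that. Section 9.1 makes any laboratory change the investigator finds clinically significant an AE, the general sentence in section 9.2 is broad, and total calcium has its own summaries, shifts, box plots and listing. What remains is narrower. Table 14.3.2 draws on the measurement listings, so investigator-reported AEs do not repair its counts. The general sentence has no limit to program and gives no AE/SAE split. The shifts run only from baseline to last dose, so a low value in mid-treatment that recovers would not show there.
- **Grading on ionized calcium alone may be deliberate.** The table cites an outside source, and ionized and total calcium are different measurements. That is fair. But the plan then needs to say how infants without an ionized value enter the calcium rates.
- **Missing data are not imputed (section 7).** One could read this as dropping infants without an ionized value from the denominator. The SAP does not say so for laboratory events, and Table 14.3.2 is specified on the safety population.

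**Conclusion.** The point holds for the table's numeric classification and for the counts built on it. The thrombocytosis SAE limit as printed is the only gap in 20 rows and would leave every count above 1000 × 10⁹/L unclassified if applied literally. Total calcium is collected and analysed but has no event limits, so infants with total calcium only would appear event-free in Table 14.3.2. That last step assumes the full safety population is the denominator.

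Three further inferences go too far. That total calcium is the exclusion measure is probable from the units but not stated. That 6 mg/dL should therefore be the event limit does not follow, since entry and event limits differ for BUN, bilirubin and creatinine. That calcium rates are biased by a known amount, or differently between dose groups, cannot be shown, because the share of infants with total calcium only is unknown.

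This is a correction worth making before lock. It does not threaten the trial's conduct.

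**What to change.** 1. **Platelets:** check the printed limit against the source of the table and correct the thrombocytosis SAE limit so that it adjoins the AE band (>1000 × 10⁹/L), as in the other high-value rows.
2. **Calcium:** before unmasking, the sponsor should choose one of two rules and write it into section 9.2. Either add a total-calcium row with limits that the sponsor sets, used when no ionized value is available; or report calcium event rates only among infants with an evaluable ionized value, and show that denominator by dose group.

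The cost is a table edit and a few lines of programming on data already collected. The downside is small: under the first rule a few more events are counted and two measurements share one event type; under the second the calcium denominator is smaller.

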9.3 Concomitant Medications of Interest

All concomitant medications, including intravenous potassium boluses or enteral electrolyte supplements, and treatments (including other diuretics) will be reported during the study drug administration period. All concomitant medications will be coded using the World Health Organization (WHO) drug classification system and presented by Anatomical Therapeutic Chemical Classification system first level (ATC1) drug classification and drug name. Frequency distributions of concomitant medications will be listed by ATC1 drug classification, drug name, and dose groups. Any diuretics used other than study furosemide during study period will be summarized separately. The cumulative dose, maximum daily dose and mean dose for caffeine at participant level will be summarized in mg/kg by dose groups. A listing of concomitant medications by participant will include start and end dates (or ongoing), and indication. Also, a listing of caffeine doses will be included.

9.4 Physical Examination

Results of the physical examination will be presented by system. Abnormal clinically significant and non-clinically significant findings will be summarized by system, visit, and dose groups. Also, the physical examination findings change from baseline to last dose will be summarized.

9.5 Special Safety Events of Interest

Hearing Loss

Hearing loss will be identified by hearing test (e.g. BAER) prior to discharge. Any failure of the hearing test (unilateral or bilateral) will be considered as hearing loss. If multiple tests are done, the last test post last study dose will be considered as the final result and any positive result during the study period will be reported. If only one hearing test is obtained, it can be considered as a final result if it was performed after the last study dose.

Nephrocalcinosis/nephrolithiasis

Nephrocalcinosis/nephrolithiasis will be determined by renal ultrasound. The summary will include nephrocalcinosis, nephrolithiasis and any of nephrocalcinosis or nephrolithiasis. A renal ultrasound is required per protocol at final study assessment. Results of standard of care renal ultrasounds will also be collected during the treatment period, follow-up period, 36-week PMA assessment. The study central radiologist (CR) will review any positive findings for nephrocalcinosis / nephrolithiasis reported by the site. If the primary study CR CONCURS with the site radiologist's findings, study image results will be documented and no further action will be taken; otherwise, a secondary study CR will review the images for final determination of results. Majority rules from up to 3 reviewers will be applied for the final renal ultrasound results. If multiple ultrasounds are received, the last ultrasound that is available post last study dose will be considered as the final result. If only one ultrasound is obtained, it can be considered as a final result if it was performed after the last study dose. In addition, any positive findings during the study period will be summarized as a separate endpoint.

Hearing loss, nephrocalcinosis and nephrolithiasis event rates will be summarized by dose groups and the percentage of participants with these events may be compared using a Fisher's exact test.

Respiratory assessment

The following information will be collected at baseline, on day 7, 14, 21, and 28 (+/- 1 day) of study drug administration, once during the follow-up period, once at 36 weeks PMA, and once at discharge:

1. Maximum F_iO_2 (sustained for > 30 minutes to account for suctioning, unless it is known to be a temporary (<2 hour) increase in F_iO_2)
2. Ventilation type:
 - a. High frequency ventilator
 - b. Conventional mechanical ventilator
 - c. NCPAP (or equivalent, see inclusion criteria in protocol synopsis table)
 - d. Cannula/Hood
 - e. None (room air with no support)

All respiratory assessments (including assessments outside the window) will be summarized by visit and dose groups.

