Dose Schedule:	
Table. N and dosing scheme
 
  
 		N	Furosemide (IV)	Furosemide (enteral)	N	Cohort N	
   
 Cohort 1	Placebo	10	1 mg/kg q 24 hours	2 mg/kg q 24 hours	30	40	
 
 Cohort 2	Placebo	10	1 mg/kg q 6 hours	2 mg/kg q 6 hours	30	40	
 
 Cohort 3	Placebo	10	2 mg/kg q 6 hours	4 mg/kg q 6 hours	30	40	
  
			N	Furosemide (IV)	Furosemide (enteral)	N	Cohort N	Cohort 1	Placebo	10	1 mg/kg q 24 hours	2 mg/kg q 24 hours	30	40	Cohort 2	Placebo	10	1 mg/kg q 6 hours	2 mg/kg q 6 hours	30	40	Cohort 3	Placebo	10	2 mg/kg q 6 hours	4 mg/kg q 6 hours	30	40
		N	Furosemide (IV)	Furosemide (enteral)	N	Cohort N																							
Cohort 1	Placebo	10	1 mg/kg q 24 hours	2 mg/kg q 24 hours	30	40																							
Cohort 2	Placebo	10	1 mg/kg q 6 hours	2 mg/kg q 6 hours	30	40																							
Cohort 3	Placebo	10	2 mg/kg q 6 hours	4 mg/kg q 6 hours	30	40																							

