3 STUDY METHODS

3.1 Overall Study Design and Plan

This study is a multi-center, randomized, placebo-controlled, dose escalating, double masked, safety study.

This study will consist of a screening for eligibility, a 28-day treatment period, a 7-day safety follow-up period, a 36-week PMA assessment and a final study assessment.

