3.2 Selection of Study Population

Premature infants (inpatient in neonatal intensive care units) will be randomized 3:1 to furosemide: placebo with increasing target doses of furosemide for each Cohort. There will be 40 randomized and dosed participants in each Cohort for a total of up to 120 participants.

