7 GENERAL ISSUES FOR STATISTICAL ANALYSIS

Descriptive statistics such as number of observations, mean, median, standard deviation, standard error, minimum and maximum will be presented by dose groups for continuous variables (such as age, weight, etc.). The dose groups will include furosemide groups (by dose level and across all dose levels), placebo group and overall. Other descriptive statistics such as counts, proportions, and/or percentages will be presented by dose groups to summarize discrete variables (such as race, sex, etc.).

Missing data will not be imputed in the non-PK analysis of this study.

Patient profile graphs showing chronologically the dosing, PK sampling, laboratory results of interest, risk of BPD, and adverse events for each participant will be developed.

All confidence intervals and tests will use $\alpha=0.05$. Analyses in this study are exploratory or descriptive in nature. No adjustments for multiplicity between endpoints are planned. Analyses will be performed using SAS Software version 9.2 or later.

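### Section 9.5 offers only an optional Fisher's exact test, with the groups compared left unstated, for hearing loss and renal calcification; a pre-specified exact dose-trend test beside it would be a cheap improvement

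*SAP*

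**What the plan says.** SAP section 3.1 describes the design: "This study is a multi-center, randomized, placebo-controlled, dose escalating, double masked, safety study". Under section 3.2, infants "will be randomized 3:1 to furosemide: placebo with increasing target doses of furosemide for each Cohort". The dose table in section 1.1 gives IV furosemide at "1 mg/kg q 24 hours", "1 mg/kg q 6 hours" and "2 mg/kg q 6 hours" for cohorts 1 to 3, with 30 infants on furosemide and 10 on placebo in each cohort.

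Section 7 defines the reporting groups: "The dose groups will include furosemide groups (by dose level and across all dose levels), placebo group and overall". It sets alpha at 0.05 without stating sidedness, plans no multiplicity adjustment between endpoints, and calls all analyses exploratory or descriptive.

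Section 9.5 says of the three toxicities: "Hearing loss, nephrocalcinosis and nephrolithiasis event rates will be summarized by dose groups and the percentage of participants with these events may be compared". The test it names for that optional comparison is Fisher's exact test. It names no contrast, trend test or interval for a difference from placebo. The only mention of drug-effect trends is in section 10.2, for the optional longitudinal model of BPD risk.

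**The concern.** Safety is the primary objective, and the trial is organised as a rising sequence of doses. The natural question about these toxicities is whether they become more frequent as dose rises. A four-group Fisher test asks only whether the rates differ somewhere, so it makes no use of the ordering. With about 30 infants per group, an analysis that ignores the ordering is more likely to miss a signal that does rise with dose. A trend test chosen after the data are seen would be post hoc under section 1 of the SAP, and the choice of scores would be open to question.

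**Working it through.** **Inputs from the SAP.** There are 30 infants per furosemide dose level (sections 1.1 and 5). Placebo is one reporting group (section 7), so 3 × 10 = 30. Alpha is 0.05 (section 7).

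**Assumptions.** Tests are two-sided, every infant is assessed after the last dose, and the event rates below are mine because the SAP gives none by dose.

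**The plan's own figures first.** The Wilson width is 2z√[p(1−p)/n + z²/(4n²)] / (1 + z²/n), with z = 1.96. For n = 30 and p = 0.1 this is 3.92 × √(0.00300 + 0.00107) / 1.128 = 0.22. The other widths are 0.28 and 0.31 (n = 30) and 0.13, 0.16 and 0.19 (n = 90). The chance of at least one event at a 5% rate is 1 − 0.95³⁰ = 0.785 and 1 − 0.95⁹⁰ = 0.990. All agree with section 5, which rests the sample size on precision and states no power for a comparison.

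**Dose scores.** Planned daily IV dose is 1 × 1 = 1, 1 × 4 = 4 and 2 × 4 = 8 mg/kg. Planned daily enteral dose is 2 × 1 = 2, 2 × 4 = 8 and 4 × 4 = 16 mg/kg. Both have the ratio 1:4:8, so scores 0, 1, 4, 8 fit either route.

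**What ignoring order means.** Take 1, 3, 5 and 8 events of 30 in dose order (17 events). The trend statistic is the sum of score × events. With scores 0-1-2-3 it is 3 + 10 + 24 = 37, against a null mean of 17 × 1.5 = 25.5. Fisher gives p = 0.0615 and the exact trend test p = 0.009. Now place the same counts as 5, 8, 1, 3. The trend statistic is 8 + 2 + 9 = 19. Fisher still gives 0.0615, while the trend test gives 0.16.

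**Power.** I enumerated all 31⁴ outcomes of the 4 × 2 table, computed the conditional exact p-value of each test for every outcome, and summed the probability of outcomes with p ≤ 0.05. The last two columns are 2 × 2 Fisher tests, which section 9.5 would equally allow. Entries are percentages.

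| Assumed rates, placebo/low/mid/high (%) | Fisher, 4 groups | Trend 0-1-2-3 | Trend 0-1-4-8 | Fisher, placebo v high | Fisher, placebo v pooled |
|---|---|---|---|---|---|
| 5/8/17/30 | 68.7 | 81.5 | 84.1 | 63.1 | 38.8 |
| 5/10/15/25 | 46.1 | 60.9 | 63.2 | 43.6 | 30.1 |
| 10/15/20/30 | 36.0 | 49.3 | 53.3 | 37.2 | 24.4 |
| 5/5/5/25 (top dose only) | 66.6 | 65.1 | 76.8 | 43.6 | 8.5 |
| 5/20/20/20 (plateau) | 36.7 | 25.2 | 19.7 | 24.1 | 47.7 |
| 5/15/25/15 (non-monotone) | 41.7 | 19.9 | 13.4 | 9.3 | 38.8 |
| 10/10/10/10 (null) | 4.1 | 3.6 | 4.5 | 0.9 | 3.0 |

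In the first three rows, the gain over four-group Fisher is 12.8, 14.8 and 13.3 points with equal spacing, and 15.4, 17.1 and 17.3 points with dose scores. At low rates (2/3/4/6%), the first three tests have about 3%, 9% and 11% power. With four-group Fisher and the 0-1-4-8 trend test both reported, the chance of at least one p ≤ 0.05 under the null is 7.1% at a 10% rate.

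**The case against.** The strongest reply is that nothing here is wrong. Fisher's test is valid for sparse binary data, the comparison is optional and exploratory, and the sample size rests on precision. The committed output, rates by ordered dose group, already lets a reader see a gradient. All of that stands, and it limits the point to an improvement.

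A reader might infer that the SAP prescribes a four-group unordered test. It does not: section 7 lists pooled furosemide among the groups, so placebo against pooled or pairwise tests fit section 9.5 equally well. These readings do not remove the concern, since both 2 × 2 tests shown have less power than the trend test in the rising scenarios.

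A reader might also infer that the trend test is simply better. It is not. With a plateau or a non-monotone pattern it loses to Fisher, and the dose scores lose more than equal spacing does. When events are rare it is still ahead in the scenario tried, but too weak to be useful.

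Two costs of the remedy also stand. Two tests without a rule on which governs raise the false-positive chance for each endpoint, and section 9.5 has several. In addition, dose levels enrol in sequence (section 4.1), so a calendar drift in event rates could look like a dose trend when placebo is pooled across cohorts. Fisher's test shares that weakness, but a steady drift is exactly what a trend test picks up.

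**Conclusion.** The point holds as a cheap improvement. Section 9.5 leaves the contrast open and names no dose-ordered analysis. If its test is run across four groups, it gives up about 13 to 17 points of power to an exact trend test in the steadily rising scenarios tried. That size depends on assumed rates, complete assessment of 30 infants per group, two-sided testing and a rate that really does rise with dose. The documents do not support calling the plan invalid or saying that a toxicity signal would be missed. They also do not support replacing Fisher's test, because the direction of the advantage depends on the shape of the dose response.

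**What to change.** In section 9.5, before unmasking:

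- Pre-specify an exact Cochran-Armitage trend test over pooled placebo and the three dose levels, two-sided, with scores fixed at 0, 1, 4, 8.
- Keep Fisher's exact test beside it and state which groups it compares.
- Report each dose group's event-rate difference from placebo with a 95% confidence interval, which is informative whatever the shape and fits the precision rationale of section 5.
- Label both tests as descriptive safety screening, and note that together they give about a 7% chance of at least one p ≤ 0.05 under the null (at a 10% rate).
- Show event rates by cohort, placebo included, so that calendar drift is not read as a dose trend. With 10 placebo infants per cohort this display is coarse.

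The cost is a few sentences, one more exact procedure and one more display. Data collection, trial conduct and clinical management do not change.
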